5.1.2 Clinical Attachment Level (CAL)

CAL is the measured distance from an invariable reference point such as cementoenamel junction (CEJ) to the bottom of pocket using the intended probe based on 6 sites per tooth (6-site measurement method) in full mouth at V1, V3 and V4. CAL is recorded in 1 mm increments. If CAL is not measurable on 1 or 2 of 6 sites on V1, the site(s) should be skipped but the tooth can be included in the assessment. If CAL is not measurable on more than 2 sites, the whole tooth should be skipped.

For each patient, the mean Full mouth CAL is calculated by the following formula,

$$\text{Full Mouth CAL (mm)} = \frac{1}{t} \sum_{i=1}^t \sum_{j=1}^{s_i} \frac{CAL_{ij}}{s_i}$$

Where CAL_{ij} is the CAL measurement of tooth i , $i = 1, \dots, t$ at the site j where $j = 1, \dots, s_i$. Note that s_i is the number of measurable sites per tooth and $s_i \geq 4$.

Confidentiality Statement

Data and information contained in this document are considered to constitute trade secrets and confidential commercial information, and the legal protections provided to such trade secrets and confidential information are hereby claimed under the provisions of applicable law. No part of this document may be publicly disclosed without the written consent of Philip Morris Products S.A

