8.2 Full Analysis Set

The Full Analysis Set (FAS) consists of all randomized patients who have at least one post-randomization product use experience, and who have at least one valid non-safety assessment after randomization. The FAS will be analysed by randomized study product.

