8.3 Per Protocol Set

The Per Protocol Set (PP) is the subset of the FAS who fulfill key compliance criteria of the protocol and have no major protocol deviation that influences the evaluability of the study data. The major protocol deviations are described in “12.1 Major Protocol Deviations”. The Per Protocol will be analyzed by randomized study product.

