9.5.1.1 Primary Analyses

Primary Analysis of Change from Baseline in PD at V4	
Population	
 • As Exposed Set For this analysis, subjects categorized in IQOS user, cigarette user or dual user will be included with initial PD \geq 4mm will be included.
	The primary analysis will be performed on the As Exposed Set using a mixed model for repeated measurements (MMRM). Estimates of difference in PD will be calculated for Cigarette User against IQOS User categories and Cigarette User against Dual User categories. The model will include the PD change from baseline as the dependent variable, adjusting for the following covariates; 
 1. Daily cigarette consumption at V1 2. Disease severity at V1 3. Full mouth PD at V1 4. Visit 5. Product use pattern (IQOS user, cigarette smoker or dual user) 6. Interaction between visit and product use

Confidentiality Statement

Data and information contained in this document are considered to constitute trade secrets and confidential commercial information, and the legal protections provided to such trade secrets and confidential information are hereby claimed under the provisions of applicable law. No part of this document may be publicly disclosed without the written consent of Philip Morris Products S.A

Primary Analysis of Change from Baseline in PD at V4

7. Average daily cigarette use at each visit
8. Interaction between Daily cigarette consumption at V1 and product use
9. Interaction between Disease severity at V1 and product use
10. Time since last SRP
11. Number of target tooth/teeth extracted
12. Number of non-measured target tooth/teeth extracted
13. Baseline tooth mobility

Site will be included as a random effect. The degrees of freedom will be adjusted by using Kenward Roger (KR) method. A Toeplitz structure (“type=toep”) will be specified as the covariance matrix. However, other covariance structures may be used in case of non-convergence. Covariates 8-12 will be assessed for adequacy in the model using a step-wise (backward) approach through the following algorithm.

1. Fit a full model using maximum likelihood with all covariates
2. Perform a likelihood ratio test for the full model and drop the covariate with the largest p-value for the likelihood ratio statistic if it is more than 0.05.
3. Drop one covariate (only covariates 7-14) and re-fit the model.

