9.5.2 Secondary Analyses

9.5.2.1 Secondary Analysis

Analysis of Change from Baseline in PD at V3 and CAL at V4 / V3	
Population	: • As Exposed Set
Contents	: The model will include the PD (or CAL) change from baseline as the dependent variable, adjusting for the following covariates; 
 • The statistical model is described in section 9.5.1. Note that “Full mouth PD at V1” will be replaced as “Full mouth CAL at V1”
Target visit	: • V3 (3 Months) for PD • V3 (3 Months) and V4 (6 Months) for CAL
Remarks	: • Statistical tests for PD at V3, CAL and V4 and V3 are performed in a sequential manner as detailed in section 9.1.8. • The same model for the primary analysis will be used with both V3 and V4 data included; PD at 3 months will be reported only if the test for PD between Cigarette User and IQOS User categories at 6 months is significant. • If the test between Cigarette User and IQOS Users Categories for PD is significant at V3, then the model with change from baseline CAL will be fitted with both V3 and V4 data and the test between CC and IQOS for CAL at V4 will be reported. • If the test between Cigarette User and IQOS User categories for CAL at V4 is significant, then the test between Cigarette User and IQOS User Categories for CAL at V3 will be reported.
Sample code	Refer to “ Primary Analysis ”
Output	15.4.7.1 Analysis of Change from Baseline in Pocket Depth (mm) at V3 with Initial Pocket Depth \geq 4 mm - As Exposed Set - 15.4.7.2 Regression Coefficients and Graphical Diagnostics of Analysis of Change from Baseline in Pocket Depth (mm) at V3- As Exposed Set - 15.4.7.3 Analysis of Change from Baseline in Clinical Attachment Level (mm) with Initial Pocket Depth \geq 4 mm - As Exposed Set -

Confidentiality Statement

Data and information contained in this document are considered to constitute trade secrets and confidential commercial information, and the legal protections provided to such trade secrets and confidential information are hereby claimed under the provisions of applicable law. No part of this document may be publicly disclosed without the written consent of Philip Morris Products S.A

Analysis of Change from Baseline in PD at V3 and CAL at V4 / V3

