9.5.2.2 Supportive Analysis for Secondary Objectives

Summary Table of Supportive/Sensitivity Analyses to Evaluate the Change from Baseline in PD at V3 / CAL at V3 and V4

Population	:	
 • Full Analysis Set • Per Protocol Set
Contents	:	
The model will include the either PD or CAL change from baseline as the dependent variable, adjusting for the following covariates;
 
 • The same model described in “Primary Analysis” will be used.
Target visit	:	
 • V3 (3 Months) for PD • V3 (3 Months)/ V4 (6 Months) for CAL
Remarks	:	
 • Statistical tests for PD at V3, CAL and V4 and V3 are performed in a sequential manner as detailed in section 9.1.8. • The same model for the primary analysis will be used with both V3 and V4 data included, PD at 3 months will be reported only if the test for PD between CC and IQOS at 6 months is significant. • If the test between Cigarette User and IQOS User categories for PD is significant at V3, then the model with change from baseline CAL will be fitted with both V3 and V4 data and the test between Cigarette User and IQOS User categories for CAL

Confidentiality Statement

Data and information contained in this document are considered to constitute trade secrets and confidential commercial information, and the legal protections provided to such trade secrets and confidential information are hereby claimed under the provisions of applicable law. No part of this document may be publicly disclosed without the written consent of Philip Morris Products S.A

Summary Table of Supportive/Sensitivity Analyses to Evaluate the Change from Baseline in PD at V3 / CAL at V3 and V4

	
at V4 will be reported.
 
 If the test between Cigarette User and IQOS User categories for CAL at V4 is significant, then the test between Cigarette User and IQOS User categories for CAL at V3 will be reported.
Sample code	Refer to " Primary Analysis "
Output	
15.4.8.1 Analyses of Change from Baseline in Clinical Attachment Level (mm) with Initial Pocket Depth \geq 4 mm - Full Analysis Set, Per Protocol Set -
 
15.4.8.2 Regression Coefficients and Graphical Diagnostics of Analysis of Change from Baseline in Clinical Attachment Level (mm) - Full Analysis Set, Per Protocol Set -

Summary Table of Supportive/Sensitivity Analyses for BoExp Geometric Mean Value

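### As written, the FAS and PP models for CAL change adjust for baseline PD but not baseline CAL, because SAP 9.5.2.2 omits the replacement made in 9.5.2.1

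*SAP*

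**What the plan says.** SAP 9.5.2.2 has one entry for both outcomes in the FAS and Per Protocol Set: "The model will include the either PD or CAL change from baseline as the dependent variable, adjusting for the following covariates". The only item under that sentence is "The same model described in “ Primary Analysis ” will be used", and the sample code also points back to the primary analysis.

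The primary model in SAP 9.5.1.1 lists 13 covariates. The third is "Full mouth PD at V1"; none is a baseline CAL value.

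For the As Exposed Set, SAP 9.5.2.1 uses the primary model too, but notes that full mouth PD at V1 "will be replaced as “Full mouth CAL at V1". Section 9.5.2.2 neither repeats this note nor refers to 9.5.2.1.

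SAP 5.1.2 has CAL measured "in full mouth at V1, V3 and V4. CAL is recorded in 1 mm increments". On grouping, SAP 8.2 states "The FAS will be analysed by randomized study product" and SAP 8.3 states "The Per Protocol will be analyzed by randomized study product".

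**The concern.** A programmer working from 9.5.2.2 would fit CAL change by randomised arm with baseline PD as the only baseline probing measure. The protocol gives a reason to want baseline CAL as well: in section 4.1 it justifies stratification partly on the ground that pre-treatment PD and CAL both influence the response to therapy. The same section describes CAL change as the endpoint of greatest clinical relevance.

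Two things are at stake. The by-arm CAL estimate may be less precise than the collected data allow. And if the arms differ by chance in baseline CAL, the model corrects for that only as far as baseline PD, severity and tooth mobility stand in for it.

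**Working it through.** **Which baseline each inferential model carries, as written**

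| Model | SAP section | Baseline covariate |
|---|---|---|
| PD change, As Exposed | 9.5.1.1 | Full mouth PD at V1 |
| CAL change, As Exposed | 9.5.2.1 | Full mouth CAL at V1 (replacement stated) |
| CAL change, FAS and PP | 9.5.2.2 | Full mouth PD at V1 (no replacement stated) |
| Biomarkers of exposure, As Exposed | 9.5.2.1 | Baseline level of the biomarker |
| Biomarkers of exposure, FAS and PP | 9.5.2.2 | As above, by reference to the 9.5.2.1 biomarker table |
| GCF mediators | 9.5.3 | Value at V2 |

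The FAS/PP CAL model is the only one that does not carry a baseline of the measure it analyses. The supportive biomarker table, next in the same section, refers back to the secondary model and so keeps the right baseline.

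**What the documents give for size.** The only sample-size figure concerns PD (protocol 12.2): difference 0.25 mm, SD 0.5 mm, one-sided 2.5%, 80% power. It reproduces: a two-sample t calculation gives 63.77, so 64 per arm, and 64 / 0.75 = 85.3, so 86 per arm and 172 in total. It says nothing about CAL, for which no SD, effect or correlation is given. The precision cost can therefore only be shown over assumed ranges.

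**First calculation.** Let r be the partial correlation of baseline CAL with CAL change, given the covariates already in the model, including baseline PD. Leaving baseline CAL out multiplies the residual variance by 1/(1 − r²) and the confidence interval width by 1/√(1 − r²).

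| r (assumed) | Variance ratio | CI width ratio |
|---|---|---|
| 0.1 | 1/0.99 = 1.010 | 1.005 |
| 0.2 | 1/0.96 = 1.042 | 1.021 |
| 0.3 | 1/0.91 = 1.099 | 1.048 |
| 0.4 | 1/0.84 = 1.190 | 1.091 |
| 0.5 | 1/0.75 = 1.333 | 1.155 |

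This compares the model as written with one that adds baseline CAL. For a replacement, each figure is an upper limit, because a model with CAL alone cannot leave less residual variance than one with both baselines.

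**Second calculation, for the replacement itself.** Assume equal CAL variance at baseline and follow-up with correlation c, a baseline PD–CAL correlation q, and that baseline PD relates to CAL change only through baseline CAL. Baseline CAL then explains (1 − c)/2 of the variance of CAL change, and baseline PD explains q² times that. The variance ratio is [1 − q²(1 − c)/2] / [1 − (1 − c)/2].

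- c = 0.7, q = 0.4: (1 − 0.16 × 0.15)/(1 − 0.15) = 0.976/0.85 = 1.148; CI width ratio 1.072.
- c = 0.9, q = 0.8: (1 − 0.64 × 0.05)/(1 − 0.05) = 0.968/0.95 = 1.019; CI width ratio 1.009.

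Over c from 0.7 to 0.9 and q from 0.4 to 0.8 the interval is about 1% to 7% wider.

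**The case against.** The strongest reply is that this is a missed cross-reference and not an analysis decision. Section 9.5.2.2 exists to support 9.5.2.1; protocol 12.7 says the secondary analyses are repeated on the FAS and PP; and SAP section 7 lists no change of CAL covariate. Section 9.5.2.1 also calls its model the same as the primary one and still makes the swap, so that phrase need not exclude it. The 9.5.1.1 model further allows covariates to be added if judged necessary.

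Most of this stands, and it makes a slip the likeliest explanation. But nothing in 9.5.2.2 restores the replacement. The open clause permits it without pre-specifying it, and under SAP 4.3.2 the statisticians' blinding ends at SAP finalisation or database lock, whichever is later. A covariate added after that could be seen as chosen with the data in view.

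It also stands that baseline PD recovers part of what is lost. Protocol 2.1 describes CAL as PD plus gingival recession, so the two baselines overlap, and severity and (unless dropped in selection) tooth mobility remain in the model.

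Several stronger readings are tempting but not supported:

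- **That the FAS result is biased.** Allocation is randomised, so omitting a baseline covariate does not bias the by-arm contrast on average.
- **That the outcome's own baseline is missing.** The outcome is CAL change in sites with initial PD of at least 4 mm; full mouth CAL averages over all measured teeth. It is a related baseline, and the replacement would not turn it into the outcome's own.
- **That the mismatch is what prevents a discrepancy with the As Exposed result from being explained.** The analyses already differ in grouping (actual use against arm), in the dual-user category, in exclusions for major deviations (not applied to the FAS) and possibly in the covariates kept by backward selection. Aligning the baseline would not remove those differences.
- **That a stated amount of power is lost.** That would borrow the PD effect and SD, and 64 per arm already allows for product switchers, whom the FAS keeps.
- **That this is the trial's main check on CAL.** Protocol 12.7 calls these analyses supportive, and CAL is reported only if PD is significant at 6 and then 3 months.

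**Conclusion.** The point holds as a correction to a supportive secondary analysis. Read literally, the FAS and PP models for CAL change use baseline PD where the As Exposed CAL model uses baseline CAL, although CAL is collected at V1 and the protocol regards it as affecting response. The cost is some expected precision and no direct adjustment for chance imbalance in baseline CAL.

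The size cannot be determined from the documents. The range of about 0.5% to 15% in interval width rests on an assumed partial correlation of 0.1 to 0.5. The lower part is more plausible given the overlap with baseline PD, and the second set of assumptions gives about 1% to 7%. The loss would be nil if baseline CAL adds nothing once the other covariates are in the model. The primary PD analysis and the sample size are unaffected.

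**What to change.** In SAP 9.5.2.2, state that the FAS and PP models for CAL change use the 9.5.2.1 covariates, with full mouth PD at V1 replaced by full mouth CAL at V1, and that the PD models keep full mouth PD at V1. The second half is worth writing out because the 9.5.2.1 note sits under a sentence covering both outcomes and, read literally, would take baseline PD out of the PD model too.

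No extra retention rule is needed: the third covariate lies outside the set open to backward removal, whichever of the two ranges given in 9.5.1.1 (8–12 or 7–14) applies.

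The cost is one sentence in the SAP, settled before unblinding. No new data or patients are required.

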9.5.3 Exploratory Analyses

Summary Table of Exploratory Analysis to Evaluate the Change in (i) Multiplex assay (MAP) (ii) Parallel Reaction Monitoring (PRM)

Population	:	
 As Exposed Set
Contents	:	
The analysis will be performed on the As Exposed Set using a mixed model for repeated measurements (MMRM).
 
The model will include the log change from baseline as the dependent variable, adjusting for the following covariates;
 
 Daily cigarette consumption Disease severity at V1 MAP/ PRM at V2 Visit Product use Interaction between visit and product use Interaction between Daily cigarette consumption at V1 and product use Average daily cigarette use at each visit Interaction between Disease severity at V1 and product use Time since last SRP Number of target tooth/teeth extracted Number of non-measured target tooth/teeth extracted Baseline tooth mobility Site will be included as a random effect. The degrees of freedom will be adjusted by using Kenward Roger (KR) method. A Toeplitz structure (“type=toep”) will be specified as the covariance matrix. However, other covariance structures may be used in case of non-convergence. Covariates 7-12 will be assessed for adequacy in the model using a step-wise (backward) approach through the following algorithm. 
 Fit a full model using maximum likelihood with all covariates Perform a likelihood ratio test for the full model and drop the

Confidentiality Statement

Data and information contained in this document are considered to constitute trade secrets and confidential commercial information, and the legal protections provided to such trade secrets and confidential information are hereby claimed under the provisions of applicable law. No part of this document may be publicly disclosed without the written consent of Philip Morris Products S.A

	
covariate with the largest p-value for the likelihood ratio statistic if it is more than 0.05.
 
3. Drop one covariate (only covariates 7-12) and re-fit the model.
 
4. Perform a likelihood ratio test and drop the covariate with the largest p-value for the likelihood ratio statistic if it is more than 0.05.
 
5. Repeat steps 2 and 3 until no more covariates can be dropped.
 
6. Refit the final model with the covariates remaining in the model and estimate PD for each product use group using the restricted likelihood method.
 
Note that other covariates may be added if deemed necessary.
 
Number of subjects included in analysis, regression coefficients, 95% CI for regression coefficient, p-value for regression coefficient, Least Squares (LS) means (Cigarette, IQOS and Dual-Users), Difference in LS Means (Cigarette vs IQOS/Dual-user) and 95% CI for Difference in LS Means will be presented.
 
 • Predicted value and observed value will be plotted.
Target visit	: 
 • V3 (3 months) • V4 (6 months)
Sample code	Refer to “ Primary Analysis ”
Output	
15.4.9.1 Exploratory Analysis of Change in Multiplex Assay - As Exposed Set -
 
15.4.9.2 Regression Coefficients and Graphical Diagnostics of Exploratory Analysis of Change in Multiplex Assay - As Exposed Set -
 
-
 
15.4.9.3 Exploratory Analysis of Change in Parallel Reaction Monitoring - As Exposed Set -
 
15.4.9.4 Regression Coefficients and Graphical Diagnostics of Exploratory Analysis of Change in Parallel Reaction Monitoring - As Exposed Set -

Summary Table of (i) MAP (ii)PRM

Population	:	
 • As Exposed Set
------------	---	--

Confidentiality Statement

Data and information contained in this document are considered to constitute trade secrets and confidential commercial information, and the legal protections provided to such trade secrets and confidential information are hereby claimed under the provisions of applicable law. No part of this document may be publicly disclosed without the written consent of Philip Morris Products S.A

Summary Table of (i) MAP (ii)PRM	
	➤ Product use pattern categories
Contents	: In addition to the contents defined in “ Descriptive statistics ”, robust measures for the center (median) and the dispersion (median absolute deviation, MAD), geometric means and CV will be presented as well.
Analysis variables	: 
 • Observed value of MAP and PRM • Change from baseline
Target visit	
 • Baseline • V3 (3 months) • V4 (6 months)
Output	15.2.9.1 Summary Table of Multiplex Assay - As Exposed Set - 15.2.9.2 Summary Table of Parallel Reaction Monitoring - As Exposed Set - 15.3.9.1 Listing of Multiplex Assay - As Exposed Set - 15.3.9.2 Listing of Parallel Reaction Monitoring - As Exposed Set - 15.1.9.1 Heatmap of Change in Multiplex Assay by Visit and Product Use Categories - As Exposed Set - 15.1.9.2 Heatmap of Change in Parallel Reaction Monitoring by Visit and Product Use Categories - As Exposed Set -

9.5.4 Safety Evaluation

9.5.4.1 Safety Reporting

9.5.4.2 Adverse Events

For AE tables, tabulations will be performed for both the number and percentage of patients experiencing an event and the number of events experienced during the study period by Medical Dictionary for Regulatory Activities (MedDRA, Version 20.0 or higher) System Organ Class (SOC) - sorted by alphabetical order, Preferred Terms (PT) - sorted by alphabetical order. If there is a change in severity for an AE for a subject, that event is counted once at the worst severity. If a subject has AEs that occurs and resolves on multiple occasions, each AE is counted once at the highest severity. Unless otherwise noted, target population will be used as denominator for frequency table.

Confidentiality Statement

Data and information contained in this document are considered to constitute trade secrets and confidential commercial information, and the legal protections provided to such trade secrets and confidential information are hereby claimed under the provisions of applicable law. No part of this document may be publicly disclosed without the written consent of Philip Morris Products S.A

All AEs will be summarized by product use group, SOC and PT. The adverse events that occurred during the study will be broken down and reported in the following ways,

- Occurrence of serious adverse events
- Severity of adverse events
- Relatedness of adverse event to study procedure and investigational product
- Adverse events leading to discontinuation

The tables below show the various ways in which adverse events will be reported for the study.

Summary Table of Adverse Events		
Population	:	
 • Safety Sets 
 ➤ Product use pattern
Contents	:	
The number and percentage of patients experiencing an adverse event and the number of adverse events during the study period.
 
The overview table 15.2.10.1 includes a summary of overall number of AEs, SAEs, severity and relation to study procedure or investigational product and response to adverse events.
 
The summary table 15.2.10.2 shows a tabulation of adverse events by SOC/PT.

Output		
15.2.10.1 Overview Table of Adverse Events - Safety Set -
 
15.2.10.2 Summary Table of Adverse Events - Safety Set -
 
15.3.10.1 Listing of Adverse Events - Safety Set -

Summary Table of Adverse Events by Severity		
Population	:	
 • Safety Sets 
 ➤ Product use pattern
Contents	:	
The number and percentage of patients experiencing an adverse event and the number of adverse events during the study period by severity. If a subject experiences the same adverse event at more than one

Confidentiality Statement

Data and information contained in this document are considered to constitute trade secrets and confidential commercial information, and the legal protections provided to such trade secrets and confidential information are hereby claimed under the provisions of applicable law. No part of this document may be publicly disclosed without the written consent of Philip Morris Products S.A

		severity then the AE will be counted only once (in the Table) with the worst severity. Any missing severity will be accounted as “severe”.
Output		15.2.10.4 Summary Table of Adverse Events by Severity - Safety Set -

Summary Table of Adverse Events Related to Product Exposure		
Population	:	
 • Safety Sets 
 ➤ Product use pattern
Contents	:	The number and percentage of patients experiencing an adverse event related to product exposure and the number of adverse events related to product exposure during the study period.
Output		15.2.10.3 Summary Table of Adverse Events Related to Product Exposure - Safety Set -

Summary Table for Expectedness of Adverse Events Related to Investigational Product		
Population	:	
 • Safety Sets 
 ➤ Product use pattern
Contents	:	The number and percentage of patients experiencing an adverse event related to an investigational product and its expectedness (Yes/No).
Output		15.2.10.8 Summary Table for Expectedness of Adverse Events Related to Investigational Product - Safety Set -

Summary Table for Relatedness of Adverse Events to Study Procedure		
Population	:	
 • Safety Sets 
 ➤ Product use pattern
Contents	:	The number and percentage of patients experiencing an adverse event related to study procedures.
Output		15.2.10.9 Summary Table for Relatedness of Adverse Events Related to Study Procedure. - Safety Set -

Confidentiality Statement

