### **Confidentiality Statement**

---

Data and information contained in this document are considered to constitute trade secrets and confidential commercial information, and the legal protections provided to such trade secrets and confidential information are hereby claimed under the applicable provisions of applicable law. No part of this document may be publicly disclosed without the written consent of Philip Morris Products S.A.

---

for both the number of patients experiencing an event and the number of events experienced during the study period.

The number and percentage of patients with clinical findings will be summarized for the Safety Set.

Incidence and frequency of concomitant medications and device events will be tabulated by exposure group.

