9.5.4.2.1 Serious Adverse Events (Including Deaths)

Summary Table of Serious Adverse Events		
Population	:	
 • Safety Sets 
 ➤ Product use pattern
Contents	:	The number and percentage of patients experiencing a serious adverse event and the number of serious adverse events during the study period.
Output		15.2.10.5 Summary Table of Serious Adverse Events - Safety Set - 15.3.10.2 Listing of Serious Adverse Events - Safety Set -

Summary Table of Adverse Events Leading to Death		
Population	:	
 • Safety Sets 
 ➤ Product use pattern
Contents	:	The number and percentage of patients experiencing an adverse event leading to death during the study period and the number of adverse events leading to death during the study period.
Output		15.2.10.6 Summary Table of Adverse Events Leading to Death - Safety Set - 15.3.10.3 Listing of Adverse Events Leading to Death - Safety Set -

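### On its plain reading, the SAP's rule for recurrent adverse events counts repeat episodes once, which conflicts with the event counts promised in the protocol and SAP

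*SAP*

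**What the plan says.** SAP 9.5.4.2 opens with a general paragraph for AE tables. By system organ class (SOC) and preferred term (PT), it promises the number and percentage of patients with an event and also "the number of events experienced during the study period". Two counting rules follow:

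- On changing grade: "If there is a change in severity for an AE for a subject, that event is counted once at the worst severity".
- On recurrence: "If a subject has AEs that occurs and resolves on multiple occasions, each AE is counted once at the highest severity".

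Neither rule is tied to a particular column or table.

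The table specifications repeat the promise of events:

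- Overall table: "The number and percentage of patients experiencing an adverse event and the number of adverse events during the study period".
- Severity table: patients and "the number of adverse events during the study period by severity". This table also has its own rule: the same AE seen at more than one grade in a subject enters once, at the worst grade.
- Product-related table: "the number of adverse events related to product exposure during the study period".
- Serious AE table (9.5.4.2.1): "the number of serious adverse events during the study period".
- Tables of AEs leading to death (9.5.4.2.1) and to discontinuation (9.5.4.2.2): event counts as well.

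The expectedness and study-procedure tables promise patient counts only. Protocol 12.8 says tabulations are made "for both the number of patients experiencing an event and the number of events experienced during the study period". SAP section 7, on changes from the protocol, mentions only the As Exposed Set and the Adherent Use Set.

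**The concern.** Counting once at the worst grade is a normal convention for patient counts. Applied to an event count, it removes what that column is there to show, namely how often the event happened.

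Protocol 12.8 makes AE data the primary assessment of safety, and Protocol 6.2 allows ad libitum use of both products. If one product-use group had the same number of affected patients as another but more episodes per patient, only the event column could show it in a summary table. A change in event counting would also depart from the protocol without being declared in SAP section 7.

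**Working it through.** The plan states no figure on this point, so there is nothing to reproduce. The check compares the texts, works out what the rule does, and adds an illustration.

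**1. Which reading is more natural.** Three features of the text bear on the recurrence sentence:

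- The sentence before it already deals with a grade change within one event. The recurrence sentence adds something new only if it is about repeat episodes.
- Grammatically, the AE is the thing that comes and goes several times. It is therefore the event type, not the episode, that is counted once.
- The severity table uses the term in the same event-type sense and also counts once, in a table that promises event numbers.

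**2. What the rule does on that reading.** Let k(i,j) be the number of separate episodes of preferred term j in patient i. Assume that the same AE means the same preferred term; the SAP does not define this.

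| Level | Patients | Events under the rule | Actual episodes |
|---|---|---|---|
| One PT | number of i with k(i,j) > 0 | number of i with k(i,j) > 0 | sum over i of k(i,j) |
| SOC or overall | number of i with any k(i,j) > 0 | number of pairs (i,j) with k(i,j) > 0 | sum over i and j of k(i,j) |

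At PT level the event count is identical to the patient count. At SOC and overall level it counts patient-by-distinct-AE pairs, which lies between the patient count and the number of episodes. The shortfall is the sum of k(i,j) − 1 over all pairs with at least one episode, so it is zero if no AE recurs.

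**3. Illustration, with assumed recurrence.** For 10 affected patients with 4 episodes each of one term, the actual total is 10 × 4 = 40 and the rule gives 10. If one group has 10 affected patients with 1 episode each and another has 10 with 3 each, the actual totals are 10 and 30. Under the rule both show 10.

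If episodes of one term follow a Poisson distribution with mean λ per patient, n patients have nλ episodes and n(1 − e^−λ) affected patients. The shortfall is 1 − (1 − e^−λ)/λ. With n = 86, the planned number per arm:

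| λ (assumed) | Episodes | Shown as events | Shortfall |
|---|---|---|---|
| 0.05 | 4.3 | 4.2 | 2.5% |
| 0.1 | 8.6 | 8.2 | 4.8% |
| 0.25 | 21.5 | 19.0 | 11.5% |
| 0.5 | 43.0 | 33.8 | 21.3% |
| 1 | 86 | 54.4 | 36.8% |
| 2 | 172 | 74.4 | 56.8% |

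The percentage does not depend on n. This matters because the Safety Set is analysed by product use, so its groups will not be the randomized arms.

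**4. What does not change.** Patient counts and percentages are the same whether a patient has one episode or several. The safety endpoint in Protocol 3.2 is incidence, and Protocol 12.7 presents it as frequencies and percentages of patients. Listing 15.3.10.1 is planned for the Safety Set. Protocol 8.2.1 has start and stop dates and times recorded for each AE, so episodes can be told apart.

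**The case against.** The best defence is the per-episode reading. The sentence begins with a plural and then speaks of each AE, so it could mean that each of several resolved episodes is counted once, at its own highest grade. That fits the sentence before it and keeps the paragraph consistent with its opening promise of events. The severity table can be used the same way: where repeats are plainly merged, the SAP uses more explicit words, and the general paragraph does not. This reading is possible and would remove the conflict, but the three features in the working make it the weaker one. Two programmers could reasonably implement different rules and report different totals, so the sentence needs correcting on either reading.

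The SAP also places detailed table descriptions in a separate shell document (SAP section 1). The shells might define the event column, but they cannot be checked here.

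Three stronger conclusions that a reader might draw are not supported:

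- That event columns repeat patient columns throughout. This holds at PT level only; above it, a patient with several distinct terms still contributes several events.
- That AE incidence is understated or safety data are lost. Patient counts are unchanged, and the listing should still show the episodes.
- That a real difference between groups will be hidden. Protocol 6.2 lists possible signs of nicotine overexposure, such as headache and dizziness, which can recur. The documents give no recurrence rate and no ground for expecting one to differ between groups.

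**Conclusion.** Wrong as written, and minor. On its plain reading, the recurrence rule conflicts with the event counts promised in the same paragraph, in Protocol 12.8 and in the overall, severity, product-related, serious AE, death and discontinuation tables. The effect is confined to the event columns of those summary tables. No efficacy analysis is touched.

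The size of the understatement cannot be derived from the documents; the 40-to-10 example and the Poisson percentages are illustrations on assumed rates. The conclusion rests on two assumptions: that the recurrence sentence refers to the event type and not the episode, and that the table shells, which were not available, do not already define the event columns differently.

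**What to change.** Replace the recurrence sentence in SAP 9.5.4.2 with a rule for each column:

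- **Patient counts:** each patient is counted once per preferred term, at the worst severity.
- **Event counts:** every separate occurrence, from start to resolution, is counted; a severity change within one occurrence is counted once, at its worst grade.

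Align the severity table's own rule with this, so that its patient column uses the patient's worst grade for the term and its event column uses each occurrence's own worst grade. Check that the table shells agree.

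The cost is a short SAP wording change and matching programming. Start and stop dates and times are already collected, so no new data are needed.
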